Final biotin concentrations after transfusion (recipient circulation) are 0.2 µg/mL and 0.04 µg/mL, days 5-7 and 35-42, respectively. Subjects will be closely monitored for evidence of transfusion reactions, and vital signs will be taken at baseline and every 15 minutes during the transfusion and then 15 minutes after the transfusion ends by qualified personnel at the Clinical Translational Research Center (CTRC) of UPMC Montefiore Hospital (MUH-CTRC).

To evaluate RBC post transfusion survival, blood samples will be taken to quantify biotin labeled RBCs pre-transfusion and at 2-4 hours, 1 month and 2 months after each transfusion. Additional blood samples will be obtained at Visit 1 for naturally occurring to anti-BioRBC antibodies and on Day 35-42 and Day 125-150 to evaluate the formation of antibodies to the biotinylated RBCs and any signs of hemolysis. The overall study design is depicted in Figure 1 below.

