### Visit 3 (Day 5-7)

This visit will be scheduled between approximately 5-7 days following blood donation in MUH-CTRC. A "Physician's Processing Request form" will be sent to the HSCLab staff via the UPMC secure email system. This form will have the subject's private health information and the study ID number that is reviewed and signed/dated by the PI or Co-I in this study. In order for the blood to be released from HSCLab to CTRC, HSCLab will need this form. The Vitalant form, "Patient

Identification Form” that is sent to HSCLab by the study team via the UPMC secure email system will contain the subject’s private health information and study ID number. In order for the blood to be released from Vitalant to HSCLab on the day of biotinylation, Vitalant will need this form.

- Brief physical examination to include vital signs (Temp, HR, RR, BP, pulse ox)
- Urine pregnancy test in women of childbearing potential
- Blood draw for whole blood sample will be sent to Wake Forest University
- Blood draw for clinical lab testing (CBC)
- Blood draw prior to transfusion to detect presence of BioRBCs. Results not needed to proceed with the study.
- Transfuse 150 mL of 5-7 days old BioRBCs
- Obtain the subject’s leftover BioRBCs in IV line/unit of blood for storage and stress hemolysis
- Vital signs (Temp, HR, RR, BP, pulse ox) approximately every 15 minutes during the transfusion and approximately 15 minutes post transfusion
- Blood draw approximately 2-4 hours post transfusion to determine baseline survival for 5-7 days old BioRBCs.
- AE assessment
- Given meal

Total blood volume drawn will be about 2 tablespoons (approximately 14 mls).

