#### Visit 4 (Day 6-8)

Subject will return approximately 24 hours ( $\pm$  4 hours) after the first blood transfusion visit to MUH-CTRC.

- Blood draw approximately 24 hours following the first transfusion visit to test survival of BioRBCs
- Blood draw for clinical lab testing (CBC)
- AE assessment

Total blood volume drawn will be about 1 tablespoon (approximately 8 mls).

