#### Visit 5 (Day 32-41)

This visit will be scheduled approximately a little over one month (ranges between 32-41 days) after completion of 1st transfusion in MUH-CTRC.

- Blood draw to test antibodies to BioRBCs. If anti-BioRBC antibodies are detected following 1st transfusion, the subject will be withdrawn from the study. A negative test result must be confirmed prior to proceeding with 2nd transfusion.
- Blood draw for Type and Cross (ABO/Rh type and antibody screen) prior to transfusion
- AE assessment

Total blood volume drawn will be about 1 tablespoon (approximately 10 mls).

Visit 6 (Day 35-42) This visit will be scheduled between approximately 35-42 days following blood donation in MUH-CTRC. A “Physician’s Processing Request form” will be sent to the HSCLab staff via the UPMC secure email system. This form will have the subject’s private health information and the study ID number that is reviewed and signed/dated by the PI or Co-I in this study. In order for the blood to be released from HSCLab to CTRC, HSCLab will need this form. The Vitalant form, “Patient Identification Form” that is sent to HSCLab by the study team via the UPMC secure email system will contain the subject’s private health information and study ID

number. In order for the blood to be released from Vitalant to HSCLab on the day of biotinylation, Vitalant will need this form.

- Brief physical examination to include vital signs (Temp, HR, RR, BP, pulse ox)
- Review medical history and demographics
- Urine pregnancy test in women of childbearing potential
- Blood draw for whole blood sample will be sent to Wake Forest University
- Blood draw for clinical lab testing (CBC)
- Blood draw prior to transfusion to detect presence of BioRBCs. Results not needed to proceed with the study.
- Transfuse 150 mL of 35-42 days old biotin-labeled RBCs
- Obtain the subject's leftover BioRBCs in IV line/unit of blood for storage and stress hemolysis
- Vital signs (Temp, HR, RR, BP, pulse ox) approximately every 15 minutes during the transfusion and approximately 15 minutes post transfusion
- Blood draw approximately 2-4 hours post transfusion to determine baseline for 35-42 days old BioRBCs.
- AE assessment
- Given meal

Total blood volume drawn will be about 2 tablespoons (approximately 14 mls).

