#### Visit 7 (Day 36-43)

Subject will return approximately 24 hours ( $\pm$  4 hours) after the second blood transfusion visit to MUH-CTRC.

- Blood draw approximately 24 hours following the second transfusion visit to test survival of BioRBCs
- Blood draw for clinical lab testing (CBC)
- AE assessment

Total blood volume drawn will be about 1 tablespoon (approximately 8 mls).

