### 2.5.2 Statistical Analysis

The primary assessment of RBC transfusion efficacy is post transfusion survival. Data from RBC recovery at 2-4 hours, 1 month and 2 months after each transfusion will be evaluated using mixed effect model (with restricted maximum likelihood variance estimator and bootstrapping) to calculate the effect of time, genetic group and their interaction on RBC survival. RBC recovery at each time point will be performed using the equation below.

$$\text{Percent survival (\%)} = \frac{\text{BioRBCs in circulation at } T_y \text{ (} 1 \leq y \leq 120 \text{ days)}}{\text{Baseline BioRBCs in circulation at } T_0 \text{ (20 min following RBC infusion)}} * 100$$

Secondary endpoints: The equation above will be used to define the 2-4hours post transfusion survival of BioRBCs. The other endpoints test for changes in RBC predisposition to hemolysis in cold storage by quantifying the rates of storage, osmotic, mechanical and oxidative hemolysis and the formation of RBC membrane-derived microvesicles. A sample size of 8 samples would detect a 10% difference in our assays' outputs with a power of 85%. We will use commercial software for statistical analyses (STATA version 15.0, StataCorp., College Station, Texas, USA). We will use mixed effect model (with restricted maximum likelihood variance estimator and bootstrapping) to calculate the effect of time, genetic group and their interaction on RBC survival. Normality tests will help to determine the appropriate transformation of outcome data. We will also use nonlinear term of time in these models (if applicable). We will use marginal test (from the primary models) to assess the effect of genetic group on 60-days and 2-4hours RBC survival separately. As a confirmatory analysis, Wilcoxon signed rank test will determine the differences between two groups for 60-days and 2-4 hours survival rate as well. The hypotheses will be tested primarily in old blood. A separate analysis will be performed in fresh blood transfusion as well. All P value <0.05 will be reported as statistically significant.

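### The percent-survival formula divides by a 20-minute sample that no visible visit schedules; confirm that it is taken, or name a sampled T0, before group results are seen

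*Combined protocol and SAP*

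**What the plan says.** Section 2.5.2 gives one formula for the outcome and states its scope: "RBC recovery at each time point will be performed using the equation below". The denominator is the labelled-cell level at T0, "20 min following RBC infusion". The printed numerator runs from day 1 to day 120. The same section then says of the early secondary endpoint: "The equation above will be used to define the 2-4hours post transfusion survival of BioRBCs". The 2-4 h value also enters the mixed model with the 1- and 2-month values, and is compared between groups by a marginal test and a Wilcoxon test. Section 2.4 builds the primary endpoint from the same three time points. The synopsis has 2-4 h survival as a secondary endpoint and in Aim 2.

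On sampling, section 2.2.1 says "blood samples will be taken to quantify biotin labeled RBCs pre-transfusion and at 2-4 hours, 1 month and 2 months after each transfusion". At Visit 3 the entry is "Blood draw approximately 2-4 hours post transfusion to determine baseline survival for 5-7 days old BioRBCs", and at Visit 6 it is "Blood draw approximately 2-4 hours post transfusion to determine baseline for 35-42 days old BioRBCs". A further draw follows each infusion: "Blood draw approximately 24 hours following the first transfusion visit to test survival of BioRBCs" (Visit 4) and "Blood draw approximately 24 hours following the second transfusion visit to test survival of BioRBCs" (Visit 7).

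Section 2.5.1 gives the planning means (75% at 30 days, 50% at 60 days) on a scale where the 24-hour value is 100%. A 1-hour survival value is named in Aim 2 of section 1.2, in section 2.1, in the secondary endpoints of section 2.4 and in the imputation model of section 2.5.3.

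**The concern.** A percentage needs a denominator that is measured. If the 20-minute sample is not taken, the outcome formula cannot be used as printed, and the analyst must substitute another draw. That substitution has consequences, because T0 decides which early losses count. A loss before T0 cancels from every later value, and the study's rationale is haemolysis after transfusion of aged stored cells.

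The 2-4 h draw is the obvious substitute, since the visit text already calls it baseline, but it is also a tested outcome. One sample cannot be both the denominator and an informative response.

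**Working it through.** **1. Inventory of draws after an infusion.** These come from sections 2.2.1 and 2.2.2 (Visits 3 to 10 and the additional draws) and Appendix A.

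| Time after infusion | Labelled-cell draw scheduled? | Use in the plan |
|---|---|---|
| about 15 min | No, vital signs only | none |
| 20 min | No | denominator (2.5.2) |
| 1 h | No | named in 1.2, 2.1, 2.4 and 2.5.3 |
| 2-4 h | Yes (Visits 3, 6) | called baseline survival or baseline; also model response, endpoint and tested outcome |
| 24 h | Yes (Visits 4, 7) | scale of the planning means; not a model time point |
| 1 and 2 months after the second infusion | Yes (Visits 8, 9) | model responses |

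Appendix A marks a post-transfusion draw at V3 and V6 without a clock time and has no 20-minute row. The additional draws are return visits over the following 3 months, so they cannot supply a same-day sample.

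**2. Numerator range.** The formula requires y between 1 and 120 days. A value at 2-4 h is below 1 day, so the formula as printed excludes the endpoint it is said to define.

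**3. If the 2-4 h draw is used as T0.** For each subject, 2-4 h survival = 100 × (value at 2-4 h) / (value at 2-4 h) = 100. All 15 + 20 = 35 subjects have 100% with SD 0. One of the three model time points and both 2-4 h tests then carry no information.

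**4. What the choice of T0 does to the later values.** The documents give no early-loss figure, so the following is an illustration on assumptions. Controls stay at 100% until 24 h, then 75% at 30 days and 50% at 60 days. Carriers lose an extra 5%, 10% or 20% once (multiplier f = 0.95, 0.90 or 0.80) and survive equally afterwards.

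- *Loss before 2-4 h.* Against 20 minutes, the 30-day difference is 75(1 − f) = 3.75, 7.5 or 15 points and the 60-day difference is 50(1 − f) = 2.5, 5 or 10 points. Against 2-4 h or 24 h, the carriers' 60-day value is 50f/f = 50, so the difference is 0. The same holds at 30 days.
- *Loss between 2-4 h and 24 h.* Against 20 minutes or 2-4 h, the 60-day difference is again 2.5, 5 or 10 points. Against 24 h it is 0, and the carriers' 2-4 h value becomes 100/f = 105.3, 111.1 or 125. That is 5.3, 11.1 or 25 points above controls.

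**5. The plan's own power figure.** Inputs from section 2.5.1: 15 vs 20 subjects, 13 points, SD 12.5. Alpha is 0.05 from section 2.5.2; two-sided is assumed. The noncentrality is 13 / (12.5 × √(1/15 + 1/20)) = 13 / 4.27 = 3.04 on 33 degrees of freedom. Power is 84.0%, matching the stated 84%. For 25 points at 60 days it is 99.99%, consistent with the stated >95%. If a change of T0 scales difference and SD by the same factor, the ratio 13/12.5 is unchanged and 30-day power stays at 84.0%.

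**The case against.** The strongest reply is that section 2.5.2 names exactly one denominator, so the plan is not undecided. That is right, and it rules out a reading that is tempting here: that the plan runs three competing references (20 minutes, 2-4 h, 24 h). The 24-hour scale belongs only to planning means taken from the literature. No section names the 2-4 h draw as T0, and baseline survival at Visit 3 may mean simply the first survival measurement.

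A reader might also infer that T0 will be picked after the data are in, or that 2-4 h survival certainly has no variance. Both follow only if no 20-minute sample exists, and the documents do not settle that. The design schematic is not shown, Appendix A gives no clock times at V3 and V6, and the laboratory procedures are separate documents.

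Two further points have force. The early-loss sizes in the illustration are assumed, and the zeros follow from dividing by a value taken after the loss. The group-by-time interaction may also be less sensitive than the point differences. On a log scale a subject's T0 shifts all of that subject's values equally and leaves the change over time intact, and section 2.5.2 leaves the transformation open. The marginal and Wilcoxon comparisons at 60 days and 2-4 h are comparisons of level, however, and they do depend on T0.

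The day 1 to 120 range is probably a notation slip, since the text applies the formula to 2-4 h. It still needs correcting. None of this supplies a scheduled denominator.

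**Conclusion.** The concern holds as a contradiction between the analysis section and the visible schedule. The primary outcome formula depends on a 20-minute value that no visit text or schedule row provides, and the first draw that is scheduled is given two incompatible roles. This is wrong as written, and it should be settled before anyone sees results by group.

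The mismatch itself is certain from the text. Its effect on the results is conditional. If the 20-minute sample is taken, only the schedule and the formula's range are wrong. If it is not, a 2-4 h T0 makes the 2-4 h tests empty, and the 60-day difference can move by 2.5 to 10 points under the assumed losses of 5% to 20%.

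A reader might infer that the trial is underpowered because the planning means are on a 24-hour scale and the formula is not. The documents do not support that. A fall in power needs an assumed early loss together with an SD that does not shrink with the mean, and the plan gives neither. The stated 84% and >95% stand, and a 60-day comparison remains computable once a sampled T0 is named.

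**What to change.** Before looking at group results, the sponsor should establish whether a 20-minute sample is taken, and record the answer.

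- **If it is taken:** add it to Visits 3 and 6 and to Appendix A, keep the formula and the 2-4 h endpoint, extend the numerator range to include 2-4 h, and stop calling the 2-4 h draw baseline. The cost is a text correction.
- **If it is not:** name one sampled draw as T0 in section 2.5.2 and use it throughout. Two fallbacks need no new visit or sample.
  - *T0 = 2-4 h.* Remove the 2-4 h value as a model response and from the marginal and Wilcoxon tests. Use the 24-hour draw at Visits 4 and 7 as the early survival measure. This keeps differences that arise between 2-4 h and 24 h.
  - *T0 = 24 h.* Test no percent-survival outcome at or before 24 h. This matches the scale of the planning means.

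The cost of either fallback is real. The primary endpoint time points in section 2.4, Aim 2 and the early secondary endpoint must be edited. The claim in section 2.5.1 of at least 80% power for the interaction must be rechecked for the changed time points. Loss before T0 must be declared unmeasured.

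In every case, align the leftover 1-hour references in sections 1.2, 2.1, 2.4 and 2.5.3 with the chosen sample, and do not mix denominators within one analysis.

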## **2.4 STUDY ENDPOINTS**

### Primary Endpoint:

The primary endpoint is the labeled red blood cell recovery rate over 60-days post transfusion (using data from 2-4 hours, 1 and 2 month) of 35-42 day stored Bio-RBCs from blood donors with specified genetic mutations, compared with control subjects without the specified mutation.

This protocol may evaluate up to eight (8) genetic mutations as independent studies, compared with pooled control groups, as well as a group of subjects on testosterone replacement therapy. The eight genetic mutations that we will evaluate may include sickle cell trait (AS), and single nucleotide polymorphisms (SNPs) in ankyrin 1 (ANK1), glucose-6-phosphate dehydrogenase X-linked (G6PD), piezo-type mechanosensitive ion channel component 1 (PIEZ01), spectrin alpha

(SPTA), extended synaptotagmin-like protein 2 (ESYT2), Myo9b, and SEC14. We may identify additional SNPs as our analysis of the REDS-III GWAS study advances that could replace one of these SNP groups and/or we identify additional non-synonymous SNPs that are associated with susceptibility to hemolysis of stored red blood cells. In addition we will evaluate 15 subjects on testosterone replacement therapy with 20 controls that are gender and race matched that are not on testosterone replacement therapy. Each group will be considered a separate study for statistical purposes. Controls will be selected based on not having any of the SNPs that will be evaluated in these studies.

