## 2.5 STATISTICAL ANALYSIS

### 2.5.1 Sample Size Determination

In healthy volunteers, the mean (SD) of 30 and 60-days RBC biotin recovery rate is 75% (12.5%) and 50% (10%) (calculated from 24-hour 100% recovery value), respectively. For our first study, evaluating patients with the sickle cell trait SNP, we expect SCD trait to reduce 30 and 60-day recovery to 62% and 25%. A sample size of 15 subjects with sickle cell trait (HbAS) and 20 control African American subjects (HbAA; 10 males and 10 females) would provide 84% power to detect a difference of 13% (SD =12.5%) for 30 days and a power of >95% to detect a difference of 25% (SD = 12.5%) for 60 days RBC recovery rate between AS and AA. This sample size has at least 80% power to detect the interaction between time and genetic group as measure of different recovery rate. We will also recruit an additional 20 Caucasian control (HbAA, 10 males and 10 females) to gain power for testing the effect of other RBC mutations identified in our genome-wide association studies of blood donors (NHLBI RBC-Omics). We will use explanatory analysis for the evaluation of post transfusion recovery of RBCs from subjects with rare variants (<10% of the population) due to a projected small number of subjects carrying such mutations. All 40 control subjects will be tested and selected to not have any of the SNPs that we are studying (listed below).

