This power calculations informs our other planned studies that will compare up to 7 additional single nucleotide polymorphisms (SNPs) patient groups of 15 each, compared with our control groups without the SNPs (n=20 race and gender matched). Successful enrollment of the sickle trait and 7 SNP groups would be 120 total subjects. The eight genetic mutations that we will evaluate may include sickle cell trait (AS), and single nucleotide polymorphisms (SNPs) in ankyrin 1 (ANK1), glucose-6-phosphate dehydrogenase X-linked (G6PD), piezo-type mechanosensitive ion channel component 1 (PIEZ01), spectrin alpha (SPTA), extended synaptotagmin-like protein 2 (ESYT2), Myo9b and SEC14. We may identify additional SNPs as our analysis of the REDS-III GWAS study advances that could replace one of these SNP groups and/or we identify additional non-synonymous SNPs that are associated with susceptibility to hemolysis of stored red blood cells. In addition, we will evaluate 15 subjects on testosterone replacement therapy with 20 controls that are gender and race matched that are not on testosterone replacement therapy.

Each study will be conducted as an independent analysis of 15 subjects with the SNP and 20 race and gender matched subjects without the SNP using power calculations estimated from the SCD trait example above.

**Biotin infusion study:** The study team will target 70 evaluable subjects. The study team will approach 86 subjects with 90% expected to agree to yield 78 subjects who will sign the biotin infusion consent. The study team expects 90% of these subjects to complete the biotin infusion study yielding the target 70 evaluable subjects. The biotin infusion subjects include 20 Whites, 20 African American without sickle cell trait, 15 African Americans with sickle cell trait, and 15 males on testosterone. In addition, 20 subjects with SNPs from the REDS-III RBC-OMICS study will be included for a total of 98 subjects to sign the biotin infusion consent and yield approximately 90 subjects who complete the study.

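### The confirmatory between-group test is named as the Wilcoxon signed-rank test, which needs pairs, but the groups are 15 carriers and 20 different people

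*Combined protocol and SAP*

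**What the plan says.** Section 2.5.2 makes a mixed-effects model the primary analysis, with time, genetic group and their interaction. It then gives two follow-up analyses at the same two time points. The first is a test from the model: "We will use marginal test (from the primary models) to assess the effect of genetic group on 60-days and 2-4hours RBC survival separately". The second is the one at issue: "As a confirmatory analysis, Wilcoxon signed rank test will determine the differences between two groups for 60-days and 2-4 hours survival rate".

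The groups are defined elsewhere:

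- **First study (section 2.5.1):** "A sample size of 15 subjects with sickle cell trait (HbAS) and 20 control African American subjects".
- **Later studies (section 2.5.1):** "Each study will be conducted as an independent analysis of 15 subjects with the SNP and 20 race and gender matched subjects without the SNP".
- **Controls (section 2.4, Primary Endpoint):** "This protocol may evaluate up to eight (8) genetic mutations as independent studies, compared with pooled control groups".
- **Testosterone group:** again 15 subjects against 20 controls matched on sex and race (sections 2.4 and 2.5.1).

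Section 3.2 adds that the HbAA controls are matched to the HbAS donors on sex and age. Power for the first study is stated in section 2.5.1: this sample "would provide 84% power to detect a difference of 13% (SD =12.5%) for 30 days", and more than 95% for 25 points at 60 days with the same SD.

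**The concern.** The signed-rank test takes one difference per pair and ranks the absolute differences, so each carrier would need one identified partner. Fifteen carriers and 20 other people do not supply that, and controls shared across several mutation studies are not tied to individual carriers.

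An analyst who reaches this sentence has two options. One is to use a different test without a documented decision. The other is to discard 5 controls and invent 15 pairs, after which the p-value depends on which controls were dropped and how the rest were paired. Either way the choice is made with the data in hand, which defeats the purpose of naming the test in advance. The same sentence serves every carrier-control comparison in the protocol.

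**Working it through.** **1. Which groups are compared?** The sentence follows directly on the model-based test of genetic group and uses the same two time points, so the groups are carriers and controls. It is not a fresh-versus-stored comparison within subjects: section 2.5.2 tests the hypotheses primarily in old blood and gives fresh blood its own analysis.

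**2. Are there pairs anywhere?** Three places could supply them, and none does.
- Matching on race and sex (section 2.5.1), or on sex and age (section 3.2), is not described as one-to-one, and 15 against 20 cannot be one-to-one.
- Same-day scheduling of a control with a carrier (section 2.2.2, RBC-OMICs blood draw visit, and section 2.5.1) concerns in vitro red cell properties, not survival after transfusion. A control may also return up to 6 times, so even those are not unique pairs.
- Pooled controls (section 2.4) point away from pairing.

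**3. Does the plan's own power figure assume pairs?** Inputs from section 2.5.1: n = 15 and 20, difference 13 points, SD 12.5. Alpha is 0.05 from section 2.5.2, taken as two-sided because the plan does not say.

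- Unpaired t-test: noncentrality = 13 / [12.5 × √(1/15 + 1/20)] = 13 / 4.27 = 3.04, with 15 + 20 − 2 = 33 degrees of freedom. Power is **84.0%**, the stated figure. At 25 points the noncentrality is 25 / 4.27 = 5.86 and power is 99.99%, consistent with the stated value above 95%.
- Paired t-test, 15 pairs, within-pair correlation ρ: noncentrality = 13 / [12.5 × √(2(1 − ρ)) / √15], with 14 degrees of freedom. At ρ = 0 this is 13 / 4.56 = 2.85 and power is **75.5%**. Assumed values of 0.3 and 0.5 give 88.6% and 96.2%.

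The documents state no correlation. A value near 0.2 would also give about 84%, so this match supports the unpaired reading but does not prove it. The group sizes and the pooled controls settle the point.

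**4. What would forcing the signed-rank test cost?** Power was simulated with normal data, SD 12.5 and 20,000 runs, comparing rank-sum on 15 against 20 with signed-rank on 15 arbitrary pairs (5 controls dropped). Dependence on the pairing was checked with 1,000 data sets and 1,000 random pairings of each, using the exact two-sided critical value W ≤ 25. The verdict was counted as depending on the pairing when between 5% and 95% of pairings gave p < 0.05.

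| True difference | Source | Rank-sum power | Signed-rank power, 15 arbitrary pairs | Verdict depends on pairing |
|---|---|---|---|---|
| 25 points | planned, 60 days | 99.98% | 99.8% | 0.9% of data sets |
| 13 points | planned for 30 days; illustration only | 81.1% | 72.8% | 50.5% |
| 10 points | assumed | 58.8% | 50.4% | 61.6% |

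With SD 10, the 60-day value that section 2.5.1 quotes for healthy volunteers, power at 25 points is 100.0% for both tests and pairing dependence is 0.0%. Repeat runs agreed to within about two percentage points on power and a few points on pairing dependence. With no true difference, type I error was 4.8% for rank-sum and 5.0% for signed-rank on pairs fixed without regard to the data. The trouble is therefore the freedom to choose pairs, and the lost controls.

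As an example, in one data set simulated at 13 points the rank-sum p-value was 0.019. The signed-rank p-value ran from below 0.001 to 0.30 over 5,000 random pairings.

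**The case against.** The strongest reply is that this is one wrong word in a supporting analysis. The primary mixed model and its test of genetic group do not use it, the sample size does not rest on it, and at the planned 60-day effect nothing measurable is lost. That stands.

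It can also be said that nobody would form arbitrary pairs: an analyst with 15 and 20 values would see the mismatch and use rank-sum. That is likely. The practical risk is then an undocumented change of a pre-specified test rather than a pairing-dependent p-value, and it is still avoidable.

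The figures at 13 and 10 points are not planned effects for this test, which is applied at 60 days and 2-4 hours only. The 5% to 95% cut-off is also a choice made for this check. Those figures show direction and should carry little weight.

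Finally, 15 against 20 is not secure for every SNP. Section 2.5.1 also plans only 20 SNP carriers in total from RBC-OMICs for infusion, and treats rare variants separately. That affects group size, not pairing: the groups would still be different people.

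None of these points supplies the pairs that the named test requires.

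**Conclusion.** The concern holds. As written, section 2.5.2 prescribes a paired test for a comparison of independent groups of unequal size, and it cannot be carried out without inventing pairs.

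The effect on conclusions is small. At the planned 60-day difference of 25 points, power is above 99% with either test, and the verdict would hang on the pairing in about 1% of data sets or fewer. The cost grows only if the true difference is well below plan. No trial-specific figure can be given for 2-4 hours, because the documents state no planned difference there.

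The simulated figures assume normal data, the protocol's SD of 12.5, two-sided 0.05, and no within-pair correlation for arbitrary pairs. The finding that the test is misnamed rests on the design text alone. It should be corrected, but it does not threaten the primary analysis.

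**What to change.** In section 2.5.2, name the Wilcoxon rank-sum (Mann-Whitney) test for the between-group comparisons at 60 days and 2-4 hours. It accepts unequal groups, so it also serves any SNP group that ends up smaller than 15. With 15 against 20 its simulated type I error is 4.8%.

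If a matched analysis was intended, the plan should define the matched sets and name a method that allows sets of unequal size. Signed-rank would suit a within-subject comparison of fresh with stored cells, but section 2.5.2 does not describe one, so it is needed only if such a comparison is added.

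The cost is one sentence. Sample size, visits, data collection and the primary model stay as they are.
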